8.1.8. Standardization of Subject Screening and Selection Panel

Selection of subjects should be based on strict adherence to screening criteria at each test

center. Two vascular surgeons at each center need to clearly document the medical reasons for reaching their conclusions and additionally identify corresponding risks for each patient.

8.1.9. Imaging Examinations

Imaging studies will include echocardiography and angiography, and CT imaging should be standardized in terms of measurement methods used, such as the angle of measurement, data to be collected, reporting modalities, etc. CT scans must be used to provide information on vascular anatomy and potential lesions. The evaluation of the examination data, a qualified third-party core laboratory should be selected to evaluate imaging data.

8.2. Trial Procedure

- 1) Signing of informed consent;
- 2) Patient screening: Patients will be screened according to the inclusion criteria and exclusion criteria;
- 3) Patient enrollment;
- 4) Selection of trial products: Investigators determine the product specifications required by each subject, and the sponsor provides the corresponding product free of charge;
- 5) Performance of surgery: Surgery will be completed by the investigator;
- 6) Postoperative follow-up: Investigators are required to perform clinical follow-ups after surgery and prior to discharge, and on Day 30 and Months 6, 12, 24, 36, 48, and 60 following surgery, with CTA follow-up required on Day 30 and Months 6 and 12 following surgery, at the sponsor's expense;
- 7) Data analysis summary: The sponsor will collect all relevant data and information and commission a third party to evaluate and manage as well as statistically and analytically summarize the data.

8.2.1. Trial Procedure Chart

Trial Procedure	Screening Period	procedure	Follow-Up				
			V3	V4	V5	V6	V7-10
Visit	V1	V2					
Days	-15~0d	0	Discharge	30 ± 7 days after	6 months ± 30 days	12 months ± 30 days	Annually ±30 days from Year

				surgery	after surgery	after surgery	2 to Year 5 post-procedure
Signing of Informed Consent Form	X						
Inclusion/E xclusion Criteria	X						
Medical History/ Demographic data	X						
Pregnancy Test	X						
Physical Examination	X	X	X				
Blood Panel	X		X				
Urine Panel	X		X				
Coagulation Function	X		X				
Liver and Kidney Function	X		X				
Clinical Symptom Assessment (Modified Rankin Scale, mRS)	X		X	X	X	X	
12-Lead ECG	X		X				
Echocardiog raphy	X						
Aortic CTA	X			X	X	X	X
Cerebral CTA	X						

or MRA							
DSA		X					
Surgical Records		X					
Medication Records	X	X	X	X	X	X	X
Adverse Event Records		X	X	X	X	X	X

Notes:

- Pregnancy Test: Women of childbearing age as well as women who are suspected of being pregnant during the trial will be subject to this test.
- Physical Examination: Heart rate, respiration, blood pressure and body temperature.
- Blood Panel: Erythrocytes, leukocytes, platelet count and hemoglobin.
- Urine Panel: pH, leukocytes, erythrocytes and proteins.
- Liver and Kidney Function: Creatinine (Cr), alanine aminotransferase (ALT), aspartate aminotransferase (AST), total bilirubin (TBIL) and direct bilirubin (DBIL)
- Coagulation Function Testing: Activated partial thromboplastin time (APTT), prothrombin time (PT), internationalized standard ratio (INR), fibrinogen (FIB), thromboplastin time (TT) and D-dimer
- Data pertaining to past medication and past medical history for the three months preceding the date on which informed consent is obtained will be collected
- The CTA measurement data obtained during the screening period shall be reviewed and confirmed by the lead investigational site before subject enrollment can be initiated.
- Before discharge (Visit 3): Refers to a visit from the postoperative to a day before discharge, and the results of the last laboratory examination before discharge are collected;
- CTA data obtained prior to surgery and at 30 ± 7 days after surgery, 6 months ± 30 days after surgery and 12 months ± 30 days after surgery will be collected;

- Concomitant medication records: medications relevant to the evaluation of the investigational device (including anticoagulants, antiplatelet agents, antihypertensives, lipid-lowering drugs, hypoglycemic drugs, antibiotics, etc.); and medications administered for underlying diseases, concomitant diseases, or adverse events.
- Adverse event records: all adverse events starting from Visit V2.
- In the event of a stroke in a subject, the modified Rankin Scale (mRS) score shall be collected at 90 days after the stroke onset.
- If feasible, laboratory data obtained within 15 days prior to subject enrollment (before signing the informed consent form), as well as aortic CTA, cerebral CTA or Magnetic Resonance Angiography (MRA), echocardiography, and 12-lead ECG data obtained within 30 days prior to signing the informed consent form, may be used for baseline assessment without repeat testing.
- Long-term follow-up CTA data shall be collected at postoperative Years 2, 3, 4 and 5 (± 30 days), with records of adverse events and concomitant medications related to adverse events.*Relevant examinations and data collection shall be performed only in patients randomized to the test group.

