Medical records from five major hospitals in Honolulu, Hawaii, covering 1969 to 1977, reported 76 patients with atherosclerotic aortic aneurysms (including 10 involving the ascending aorta or aortic arch and 66 descending thoracic aortic aneurysms), with a mean age of 69 years and an estimated natural annual mortality of approximately 35%²⁴. A 2002 database from Yale University documented the natural history of 1,600 patients with thoracic aortic aneurysms: once the thoracic aortic diameter reached 6 cm, 31% of patients experienced aortic rupture or dissection; when the descending aortic diameter reached 7 cm, the risk of rupture or dissection increased to 43%¹¹, with a mortality rate of up to 90% for such events. Prognoses are even poorer for surgically high-risk patients with arch-located aneurysms. Regarding penetrating aortic ulcers (PAU), the Chinese Expert Consensus on the Diagnosis and Management of Acute Aortic Syndromes (2021 Edition) recommends proactive surgical or endovascular repair for symptomatic PAUs, or those with a diameter > 20 mm or depth > 10 mm, due to the high risk of progression to pseudoaneurysm or rupture²⁵. Published literature reports a natural annual mortality of 26.7% among patients with penetrating aortic ulcers²⁶. The European Association for Cardio-Thoracic Surgery (EACTS) and the European Society for Vascular Surgery (ESVS) acknowledge that stroke remains a major complication during aortic arch endovascular repair, with reported rates up to 14%²⁷⁻²⁹.

Measures to Reduce and Eliminate Bias

- 1) The clinical trial will be conducted in accordance with the trial protocol, national medical device clinical trial regulations and GCP principles as well as the company's standard operating procedures (SOP).
- 2) This clinical trial is a single-arm objective performance criterion study conducted simultaneously at multiple clinical centers across China. Subjects will be enrolled in accordance with the inclusion and exclusion criteria specified in the protocol. The enrolled study population shall maintain consistency with those investigated in previous studies, to minimize selection bias caused by incomparable baseline populations to the greatest extent possible.

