8.2.2. Trial Conduct

1) Visit 1: Screening Period (Day -15 to 0)

After the subject signs the informed consent form, baseline information and baseline examinations shall be collected, and screening shall be performed according to the inclusion and exclusion criteria. Eligible screened subjects will complete enrollment registration. The specific collected items are as follows:

- Demographic information, including age, gender, height, weight
- Physical examination data, including heart rate, respiration, blood pressure and body temperature
- Family history and previous medical history, including surgical history, concomitant diseases, concomitant medications and medical treatments
- Routine laboratory testing:
 - o Blood panel: Erythrocytes, leukocytes, platelet count and hemoglobin

- o Urine panel: pH, leukocytes, erythrocytes and proteins
- o Liver and kidney function: Creatinine, alanine aminotransferase (ALT), aspartate aminotransferase (AST), total bilirubin (TBIL) and direct bilirubin (DBIL)
- o Coagulation function: Activated partial thromboplastin time (APTT), prothrombin time (PT), internationalized standard ratio (INR), fibrinogen (FIB), thromboplastin time (TT) and D-dimer
- Pregnancy test (for female patients of childbearing age)
- Clinical Symptom Assessment (Modified Rankin Scale, mRS)
- 12-Lead ECG
- CTA angiography
- Cerebral CTA or MRA
- Echocardiography examination
- Concomitant medications

2) Visit 2: Intraoperative (0 day)

Record the procedural details; the specific collected items are as follows:

- Physical examination data
- DSA imaging data
- Surgery-related records (selection of stent type, arterial access, deployment, Interventional operation time (the time the sheath enters the body to the time the sheath is pulled out of the body), immediate success, etc.)
- Concomitant medications
- Adverse events
- Device defects

3) Visit 3: Before discharge

- Physical examination
- Blood panel: Erythrocytes, leukocytes, platelet count and hemoglobin
- Urine panel: pH, leukocytes, erythrocytes and proteins
- Liver and kidney function: Creatinine, alanine aminotransferase (ALT), aspartate

aminotransferase (AST), total bilirubin (TBIL) and direct bilirubin (DBIL)

- Coagulation function: Activated partial thromboplastin time (APTT), prothrombin time (PT), internationalized standard ratio (INR), fibrinogen (FIB), thromboplastin time (TT) and D-dimer
- Clinical Symptom Assessment (Modified Rankin Scale, mRS)
- 12-Lead ECG

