- Concomitant medications
- Adverse events
- Device defects

4) Visit 4: (30 ± 7 days after surgery)

This visit will be a post-discharge follow-up visit with the following information collected from the subject:

- Clinical Symptom Assessment (Modified Rankin Scale, mRS)
- Concomitant medications
- CTA angiography (aortic diameter, thrombosis status, branch vessel patency, arterial perfusion, etc.)
- Adverse events
- Device defects

5) Visit 5: (6 months \pm 30 days after surgery)

This visit will be a post-discharge follow-up visit with the following information collected from the subject:

- Clinical Symptom Assessment (Modified Rankin Scale, mRS)
- CTA angiography (aortic diameter, thrombosis status, branch vessel patency, arterial perfusion, etc.)
- Concomitant medications
- Adverse events
- Device defects

6) Visit 7, 8, 9, 10: (24 to 60 months \pm 30 days after the procedure)

This visit will be a post-discharge follow-up visit with the following information collected from the subject:

- CTA angiography (aortic diameter, thrombosis status, branch vessel patency, arterial perfusion, etc.)
- Adverse events and concomitant medications related to adverse events

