9.4.2. Statistical Methodology and Analysis

1) General Principles

For quantitative variables, mean, standard deviation, median, minimum, maximum, lower quartile (Q1), and upper quartile (Q3) will be calculated. For categorical variables, the number and percentage of subjects in each category will be presented.

Comparison of general characteristics between the two groups will be analyzed using appropriate methods according to the type of variables. Between-group comparisons of quantitative data will be performed using the independent samples t-test (for homogeneous variance and normal distribution) or the Wilcoxon rank-sum test, depending on the data distribution. Categorical data will be analyzed using the chi-square test or Fisher's exact test (if the chi-square test is not applicable). Ordinal data will be analyzed using the Wilcoxon rank-sum test or the CMH test.

2) Completion Status and Demographic Analysis

The number of enrollments and completions for each center will be summarized and a list of fallout cases as well as a detailed list of reasons for non-completion will be created. Patients' demographic characteristics (age, sex, etc.), relevant medical history treatment, etc. will be described. A demographic analysis will be performed based on an FAS analysis set.

3) Primary Endpoints

Primary Endpoint: The incidence of all-cause death or major stroke within 12 months after the procedure. All-cause death includes cardiac death, non-cardiac death, and death of unknown cause. Major stroke is defined as a modified Rankin Scale (mRS) score ≥ 2 assessed at 90 days after stroke onset. The hypothesis testing is specified as follows:

Null Hypothesis: $H_0: P_T - P_C \leq \Delta$

Alternative Hypothesis: $H_1: P_T - P_C > \Delta$

$\alpha = 0.025$ (single tail)

At the significance level of $\alpha = 0.025$ (one-sided) and statistical power of $1 - \beta = 0.8$, the incidence rate of all-cause mortality or major stroke within 12 months post-procedure shall be statistically described, and its two-sided 95% confidence interval (95% CI) shall be estimated. The upper limit of the 95% CI

shall be compared with the Objective Performance Criteria (OPC). Statistical conclusions will then be drawn accordingly. If the upper limit of the 95% CI is lower than the objective performance criterion P_0 , the primary endpoint shall meet the trial requirements, and the investigational device can be considered to satisfy the requirements for clinical application.

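### Major stroke reaches the primary endpoint only after the site declares a stroke, and the mRS scheduled at discharge, 30 days, 6 months and 12 months is not linked to finding one (cheap improvement)

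*Protocol*

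**What the plan says.** Section 9.4.2 gives the primary endpoint as "The incidence of all-cause death or major stroke within 12 months after the procedure" and adds: "Major stroke is defined as a modified Rankin Scale (mRS) score ≥ 2 assessed at 90 days after stroke onset". The result passes if the upper limit of the two-sided 95% confidence interval lies below the objective performance criterion P0.

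What is scheduled to detect a stroke is set out in sections 8.2.1 and 8.2.2:

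- **Physical examination**, at Visits 1, 2 and 3 only, defined in the chart notes as "Physical Examination: Heart rate, respiration, blood pressure and body temperature".
- **Brain imaging**, listed as "Cerebral CTA or MRA", at screening only. Later imaging is DSA during the procedure and aortic CTA.
- **mRS**, marked in the chart at Visits 1, 3, 4, 5 and 6. No text says what follows if the score rises.
- **90-day mRS**, conditional on a known event: "In the event of a stroke in a subject, the modified Rankin Scale (mRS) score shall be collected at 90 days".

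Section 8.2 says "Surgery will be completed by the investigator" and also gives the clinical follow-up to investigators. Section 14.4.1 has investigators record all adverse events. The third-party core laboratory in section 8.1.9 evaluates imaging data. No independent neurological assessment or stroke adjudication is described. Section 8.1.2 itself reports the view that "stroke remains a major complication during aortic arch endovascular repair", with rates up to 14%.

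**The concern.** Counting a major stroke takes two steps: someone recognises a stroke, and then the 90-day mRS is scored. The protocol fixes the second step and leaves the first to general adverse-event recording by unblinded site staff. The one repeated instrument that could show a missed stroke is the mRS at Visits 3 to 6, and it stands apart from the endpoint.

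The direction of error is known. A survivor with an undeclared major stroke counts as event-free. The comparator is a constant, so no control arm loses events in parallel. Missed strokes can only help the device meet P0. The ischemic stroke component of the 30-day major adverse event rate (section 8.1.7) is exposed in the same way.

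**Working it through.** **The plan's own figure.** Section 8.1.4.8 gives 72 valid cases and 20% dropout: 72 / (1 − 0.20) = 90, as stated. The 72 cannot be checked, because P0 and the expected rate are redacted.

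**Effect of one missed event.** 1 / 90 = 1.1 percentage points off the observed rate. This applies to survivors only; a subject who dies within 12 months is an event anyway.

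**Illustration of the false-pass probability.**

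Inputs from the protocol: n = 90; pass if the upper two-sided 95% limit is below P0.

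Assumptions:
- P0 between 25% and 40%.
- An exact (Clopper-Pearson) limit.
- A true composite rate equal to P0, so every pass is false.
- A component s = 7% of subjects with major stroke who would not otherwise count as events.
- A share m of that component undeclared, between 10% and 30%.

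The 7% is half of the 14% quoted in section 8.1.2, because that figure is a maximum and is not stated to be major stroke.

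Formula: let c be the largest event count whose upper limit is below P0. The false-pass probability is P(X ≤ c) with X ~ Binomial(90, P0 − s·m). For P0 = 25% and m = 30%, the observed rate is 0.25 − 0.07 × 0.30 = 0.229 and c = 14, giving 5.8%.

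| Assumed P0 | c | m = 0 | m = 10% | m = 20% | m = 30% |
|---|---|---|---|---|---|
| 25% | 14 | 2.2% | 3.1% | 4.3% | 5.8% |
| 30% | 18 | 2.2% | 3.1% | 4.2% | 5.7% |
| 35% | 22 | 2.1% | 2.9% | 4.0% | 5.3% |
| 40% | 26 | 1.9% | 2.6% | 3.5% | 4.7% |

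The range is 1.9-2.2% with full ascertainment and 2.6-5.8% with 10-30% undeclared, against a nominal one-sided 2.5%. In events, the component is 0.07 × 90 = 6.3 subjects, of whom 0.6 to 1.9 would be undeclared.

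**The case against.** The strongest reply is that the protocol already has a net for strokes. All adverse events must be recorded whatever their relation to the device (sections 14.1 and 14.4.1). Monitors confirm that they are (section 8.4, item 6). Section 10.7 adds source data verification and medical review. Subjects are scored for disability four times after surgery, and a severely disabling stroke is hard to overlook. Edit checks may also sit in the data verification plan, which is not shown.

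Much of this stands. It limits the exposure mainly to strokes near mRS 2, which Annex 2 calls slight disability and which can be put down to age, comorbidity or recovery from surgery. It does not close the gap: source verification compares records with records and cannot find a stroke that was never diagnosed. An unseen data plan may contain a cross-check, but the rule on what prompts a stroke assessment for the primary endpoint belongs in the protocol.

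The OPC may also rest on studies that under-recorded stroke in a similar way. P0 would then already carry part of the bias and the net effect would be smaller. Its derivation is not visible, so this can be neither confirmed nor excluded.

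Two stronger readings are tempting, and the documents do not support them:

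- **That stroke is found only if the implanting operator reports it.** Section 21.4, item 3, lets follow-up and adverse-event handling be delegated to other trained investigators. The supportable wording is that recognition rests with unblinded site investigators.
- **That the major-stroke component is 14%.** With that value and 20-30% undeclared, the same calculation gives 6.2-13.5%. But this takes an upper bound for all stroke as the major-stroke rate and ignores overlap with death.

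**Conclusion.** The point holds as a cheap improvement. The protocol leaves recognition of a primary-endpoint component to site declaration, schedules no neurological examination or brain imaging after screening, and does not use the mRS it already collects to check for missed strokes.

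The direction of bias, in favour of the device, follows from the single-arm comparison with a fixed P0. The size does not follow from the documents. The 2.6-5.8% false-pass range rests on assumed values for P0, the major-stroke component and the undeclared share, and on OPC sources with full ascertainment.

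A reader might infer that any unexplained mRS rise should be scored as a stroke. That goes too far. It would make a diagnosis by rule and widen the primary endpoint beyond its definition in sections 8.1.5 and 9.4.2, against a criterion whose derivation cannot be seen.

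**What to change.** 1. In the notes to section 8.2.1, state that a rise in mRS from Visit 1 to a score of 2 or more at any of Visits 3 to 6, with no declared stroke, opens a data query. The site documents the cause of the rise and whether a stroke was considered. If the site then declares a stroke, the existing 90-day mRS rule applies.
2. Leave the primary endpoint definition unchanged.
3. List all subjects with such a rise and no declared stroke. As a sensitivity analysis only, repeat the comparison with P0 counting as events those with no documented alternative cause.

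The cost is one edit check, a short paragraph and one table, with no new visits, staff or imaging. The downside is extra queries, chiefly at Visit 3, when patients are still recovering from surgery and a temporary rise in mRS is to be expected.

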8.2.2. Trial Conduct

1) Visit 1: Screening Period (Day -15 to 0)

After the subject signs the informed consent form, baseline information and baseline examinations shall be collected, and screening shall be performed according to the inclusion and exclusion criteria. Eligible screened subjects will complete enrollment registration. The specific collected items are as follows:

- Demographic information, including age, gender, height, weight
- Physical examination data, including heart rate, respiration, blood pressure and body temperature
- Family history and previous medical history, including surgical history, concomitant diseases, concomitant medications and medical treatments
- Routine laboratory testing:
 - o Blood panel: Erythrocytes, leukocytes, platelet count and hemoglobin

- o Urine panel: pH, leukocytes, erythrocytes and proteins
- o Liver and kidney function: Creatinine, alanine aminotransferase (ALT), aspartate aminotransferase (AST), total bilirubin (TBIL) and direct bilirubin (DBIL)
- o Coagulation function: Activated partial thromboplastin time (APTT), prothrombin time (PT), internationalized standard ratio (INR), fibrinogen (FIB), thromboplastin time (TT) and D-dimer
- Pregnancy test (for female patients of childbearing age)
- Clinical Symptom Assessment (Modified Rankin Scale, mRS)
- 12-Lead ECG
- CTA angiography
- Cerebral CTA or MRA
- Echocardiography examination
- Concomitant medications

2) Visit 2: Intraoperative (0 day)

Record the procedural details; the specific collected items are as follows:

- Physical examination data
- DSA imaging data
- Surgery-related records (selection of stent type, arterial access, deployment, Interventional operation time (the time the sheath enters the body to the time the sheath is pulled out of the body), immediate success, etc.)
- Concomitant medications
- Adverse events
- Device defects

3) Visit 3: Before discharge

- Physical examination
- Blood panel: Erythrocytes, leukocytes, platelet count and hemoglobin
- Urine panel: pH, leukocytes, erythrocytes and proteins
- Liver and kidney function: Creatinine, alanine aminotransferase (ALT), aspartate

aminotransferase (AST), total bilirubin (TBIL) and direct bilirubin (DBIL)

- Coagulation function: Activated partial thromboplastin time (APTT), prothrombin time (PT), internationalized standard ratio (INR), fibrinogen (FIB), thromboplastin time (TT) and D-dimer
- Clinical Symptom Assessment (Modified Rankin Scale, mRS)
- 12-Lead ECG
- Concomitant medications
- Adverse events
- Device defects

4) Visit 4: (30 ± 7 days after surgery)

This visit will be a post-discharge follow-up visit with the following information collected from the subject:

- Clinical Symptom Assessment (Modified Rankin Scale, mRS)
- Concomitant medications
- CTA angiography (aortic diameter, thrombosis status, branch vessel patency, arterial perfusion, etc.)
- Adverse events
- Device defects

5) Visit 5: (6 months \pm 30 days after surgery)

This visit will be a post-discharge follow-up visit with the following information collected from the subject:

- Clinical Symptom Assessment (Modified Rankin Scale, mRS)
- CTA angiography (aortic diameter, thrombosis status, branch vessel patency, arterial perfusion, etc.)
- Concomitant medications
- Adverse events
- Device defects

6) Visit 7, 8, 9, 10: (24 to 60 months \pm 30 days after the procedure)

This visit will be a post-discharge follow-up visit with the following information collected from the subject:

- CTA angiography (aortic diameter, thrombosis status, branch vessel patency, arterial perfusion, etc.)
- Adverse events and concomitant medications related to adverse events

